[Part 1 of 2 of the document. The other parts are not shown.]

Amendment 2.2 (Japan) 30 AUG 2021

Overall Rationale for the Amendment:

Update necessitated from reconsideration of andexanet dosage in edoxaban 15-30 mg treated Japanese patients. High-dose andexanet will be administered to these patients.

Section # and Name	Description of Change	Brief Rationale
PROTOCOL SYNOPSIS Test Product, Dose, and Mode of Administration	Changed andexanet alfa dose in Edoxaban 15-30 mg treated patients. <Amendment 2.1 (Japan)> Last dose of FXa inhibitor: < 8 hours - Edoxaban 15-30 mg (ONLY for VTE prophylaxis for patients undergoing orthopedic surgery of the lower limbs): Low dose andexanet alfa - Edoxaban 30 mg-60 mg: High dose andexanet alfa <Amendment 2.2 (Japan)> Last dose of FXa inhibitor: < 8 hours - Edoxaban 15 mg-60 mg: High dose andexanet alfa	In study 16-508, there was no statistically significant difference in the reduction in anti-fXa activity between the andexanet low dose group and placebo group in healthy Japanese subjects who took 30 mg of edoxaban. Therefore, in edoxaban 15-30 mg treated patients, high-dose andexanet is considered to ensure the reversal effect without any specific risk. Thus, the andexanet dose changed to high dose.
6.2 Dosing and Administration Table 2	Same as above	Same as above
9.2.2. Assessment of Causal Relationship	Deleted.	Deleted due to the Administrative Change Letter on 01APR2021.

Amendment Rationale:

The amendment is prepared for executing the study under the regulatory requirements and medical practice in Japan. This country-specific amendment changed a part of the protocol contents and applies to all subjects enrolled in Japan.

Changes to the Protocol:

Page	Protocol Section	Revised Protocol Text																	
22	PROTOCOL SYNOPSIS Test Product, Dose, and Mode of Administration	Revised, deleted, and Added the following underlined parts.																	
		
Before:
 
  
 Andexanet Dose	Timing of Last Dose of FXa Inhibitor	Initial Dose	Extended Infusion	
 
 Initial IV Bolus	Initial Follow-on IV Infusion	
   
 Low Dose	 
≥ 8 hours OR < 8 hours for
 
 Rivaroxaban 10 mg Apixaban 2.5-5 mg Enoxaparin 40 mg Edoxaban 30 mg 	400 mg at a target rate of 30 mg/min	4 mg/min for at least 120 minutes irrespective of the duration of surgery	Extended infusion (beyond 120 minutes) may be administered at 4 mg/min (low-dose) for up to 4 additional hours*	
 
 High Dose	 
< 8 hours
 
 Rivaroxaban ≥ 10 mg Apixaban > 5 mg Enoxaparin > 40 mg Edoxaban 60 mg 
OR
 
>15 hours or unknown time
 
 Local anti-fXa > 100 ng/mL (0.5 IU/mL for enoxaparin) 	800 mg at a target rate of 30 mg/min	8 mg/min for at least 120 minutes irrespective of the duration of surgery		
  
			Andexanet Dose	Timing of Last Dose of FXa Inhibitor	Initial Dose		Extended Infusion	Initial IV Bolus	Initial Follow-on IV Infusion	Low Dose	
≥ 8 hours OR < 8 hours for
 
 Rivaroxaban 10 mg Apixaban 2.5-5 mg Enoxaparin 40 mg Edoxaban 30 mg 	400 mg at a target rate of 30 mg/min	4 mg/min for at least 120 minutes irrespective of the duration of surgery	Extended infusion (beyond 120 minutes) may be administered at 4 mg/min (low-dose) for up to 4 additional hours*	High Dose	
< 8 hours
 
 Rivaroxaban ≥ 10 mg Apixaban > 5 mg Enoxaparin > 40 mg Edoxaban 60 mg 
OR
 
>15 hours or unknown time
 
 Local anti-fXa > 100 ng/mL (0.5 IU/mL for enoxaparin) 	800 mg at a target rate of 30 mg/min
Andexanet Dose	Timing of Last Dose of FXa Inhibitor	Initial Dose		Extended Infusion															
		Initial IV Bolus	Initial Follow-on IV Infusion																
Low Dose	
≥ 8 hours OR < 8 hours for
 
 Rivaroxaban 10 mg Apixaban 2.5-5 mg Enoxaparin 40 mg Edoxaban 30 mg 	400 mg at a target rate of 30 mg/min	4 mg/min for at least 120 minutes irrespective of the duration of surgery	Extended infusion (beyond 120 minutes) may be administered at 4 mg/min (low-dose) for up to 4 additional hours*															
High Dose	
< 8 hours
 
 Rivaroxaban ≥ 10 mg Apixaban > 5 mg Enoxaparin > 40 mg Edoxaban 60 mg 
OR
 
>15 hours or unknown time
 
 Local anti-fXa > 100 ng/mL (0.5 IU/mL for enoxaparin) 	800 mg at a target rate of 30 mg/min	8 mg/min for at least 120 minutes irrespective of the duration of surgery																

Page	Protocol Section	Revised Protocol Text				
		After:				
		Andexanet Dose	Timing of Last Dose of FXa Inhibitor	Initial Dose		Extended Infusion
		Low Dose	≥ 8 hours OR < 8 hours for 
 · Apixaban 2.5-5 mg · Enoxaparin 40 mg 	400 mg at a target rate of 30 mg/min	4 mg/min for at least 120 minutes irrespective of the duration of surgery	Extended infusion (beyond 120 minutes) may be administered at 4 mg/min (low-dose) for up to 4 additional hours*
		High Dose	< 8 hours 
 · Rivaroxaban ≥ 10 mg · Apixaban > 5 mg · Enoxaparin > 40 mg · Edoxaban 15 mg-60 mg OR >15 hours or unknown time 
 · Local anti-fXa > 100 ng/mL (0.5 IU/mL for enoxaparin) 	800 mg at a target rate of 30 mg/min	8 mg/min for at least 120 minutes irrespective of the duration of surgery	

Note: Enoxaparin is out of scope in Japan.

Page	Protocol Section	Revised Protocol Text			
54	6.2 Dosing and Administration Table 2	Revised, deleted, and Added the following underlined parts. Before: Table 2: Andexanet Dosing Paradigm and Criteria for Extended Treatment or Re-Dosing			
Dose	Timing of Last Dose of FXa Inhibitor	Initial IV Bolus	Follow-On IV Infusion	Extended Infusion	
Low Dose	
≥ 8 hours OR < 8 hours for
 
 Rivaroxaban 10 mg Apixaban 2.5-5 mg Enoxaparin 40 mg Edoxaban 30 mg 	400 mg at a target rate of 30 mg/min	4 mg/min for at least 120 minutes (480 mg total) irrespective of the duration of surgery	The infusion may be extended beyond 120 minutes at a rate of 4 mg/min (low-dose) for up to 4 additional hours.	
High Dose	
< 8 hours
 
 Rivaroxaban > 10mg Apixaban > 5mg Enoxaparin > 40mg Edoxaban 60 mg 
OR
 
> 15 hours or unknown time
 
 Local anti-fXa >100 ng/mL (0.5 IU/mL for enoxaparin) 	800 mg at a target rate of 30 mg/min	8 mg/min for at least 120 minutes (960 mg total) irrespective of the duration of surgery		

a. Initial Bolus must be completed prior to start of surgery (initial skin incision).
 
b. Initial dosing (bolus + 120 min infusion) should be completely administered regardless of surgery length.
 
c. Infusion should continue throughout the duration of surgery, (defined as skin incision to skin closure or equivalent milestone).
					

Page	Protocol Section	Revised Protocol Text																			
		
After:
 
Table 2: Andexanet Dosing Paradigm and Criteria for Extended Treatment or Re-Dosing
 
  
 Dose	Timing of Last Dose of FXa Inhibitor	Initial IV Bolus	Follow-On IV Infusion	Extended Infusion	
   
 Low Dose	 
≥ 8 hours
 
OR
 
< 8 hours for
 
 · Apixaban 2.5-5 mg · Enoxaparin 40 mg 	400 mg at a target rate of 30 mg/min	4 mg/min for at least 120 minutes (480 mg total) irrespective of the duration of surgery	The infusion may be extended beyond 120 minutes at a rate of 4 mg/min (low-dose) for up to 4 additional hours.	
 
 High Dose	 
< 8 hours
 
 · Rivaroxaban ≥ 10 mg · Apixaban > 5 mg · Enoxaparin > 40 mg · Edoxaban 15 mg-60 mg 
OR
 
> 15 hours or unknown time
 
 · Local anti-fXa > 100 ng/mL (0.5 IU/mL for enoxaparin) 	800 mg at a target rate of 30 mg/min	8 mg/min for at least 120 minutes (960 mg total) irrespective of the duration of surgery		
  
 
Note: Enoxaparin is out of scope in Japan.
 
 Initial Bolus must be completed prior to start of surgery (initial skin incision). Initial dosing (bolus + 120 min infusion) should be completely administered regardless of surgery length. Infusion should continue throughout the duration of surgery, (defined as skin incision to skin closure or equivalent milestone). 	Dose	Timing of Last Dose of FXa Inhibitor	Initial IV Bolus	Follow-On IV Infusion	Extended Infusion	Low Dose	
≥ 8 hours
 
OR
 
< 8 hours for
 
 · Apixaban 2.5-5 mg · Enoxaparin 40 mg 	400 mg at a target rate of 30 mg/min	4 mg/min for at least 120 minutes (480 mg total) irrespective of the duration of surgery	The infusion may be extended beyond 120 minutes at a rate of 4 mg/min (low-dose) for up to 4 additional hours.	High Dose	
< 8 hours
 
 · Rivaroxaban ≥ 10 mg · Apixaban > 5 mg · Enoxaparin > 40 mg · Edoxaban 15 mg-60 mg 
OR
 
> 15 hours or unknown time
 
 · Local anti-fXa > 100 ng/mL (0.5 IU/mL for enoxaparin) 	800 mg at a target rate of 30 mg/min	8 mg/min for at least 120 minutes (960 mg total) irrespective of the duration of surgery					
Dose	Timing of Last Dose of FXa Inhibitor	Initial IV Bolus	Follow-On IV Infusion	Extended Infusion																	
Low Dose	
≥ 8 hours
 
OR
 
< 8 hours for
 
 · Apixaban 2.5-5 mg · Enoxaparin 40 mg 	400 mg at a target rate of 30 mg/min	4 mg/min for at least 120 minutes (480 mg total) irrespective of the duration of surgery	The infusion may be extended beyond 120 minutes at a rate of 4 mg/min (low-dose) for up to 4 additional hours.																	
High Dose	
< 8 hours
 
 · Rivaroxaban ≥ 10 mg · Apixaban > 5 mg · Enoxaparin > 40 mg · Edoxaban 15 mg-60 mg 
OR
 
> 15 hours or unknown time
 
 · Local anti-fXa > 100 ng/mL (0.5 IU/mL for enoxaparin) 	800 mg at a target rate of 30 mg/min	8 mg/min for at least 120 minutes (960 mg total) irrespective of the duration of surgery																		

25 May 2021

Protocol: 19-515 Protocol Amendment #2: 20 July 2020

Administrative Change Letter #2

Reason for Letter: Provide clarification on the appropriate delegation of Investigator responsibilities and exploratory endpoint

To those sites participating in the above named and numbered clinical study, this letter serves to inform you about the following administrative update to the above referenced protocol version.

Clarification: Assessment of hemostatic efficacy

The current protocol states that the surgeon is responsible for determining the achievement of hemostatic efficacy according to the intraoperative hemostasis categories provided in Table 3 of Section 11.5.1. This administrative change letter serves to inform the study sites that the investigator (Principal investigator or sub-investigator as listed on the site delegation log) will be responsible for evaluating the endpoint of hemostatic efficacy. The investigator will consult with the research team and surgical team, if applicable, and will be responsible for interpretation of the endpoint prior to completing the hemostatic efficacy form. The investigator will also assess adverse events and provide oversight for study drug administration and monitoring of patients according to the protocol.

The attached hemostatic efficacy form has to be filled in for all patients which will serve a source document and also be provided to endpoint adjudication committee.

Rationale: Investigators have the required protocol and Good Clinical Practice training to participate in the evaluation of hemostatic efficacy, oversight of study drug administration, and assessment and monitoring of adverse events.

Clarification: Exploratory Endpoint

The current protocol incorrectly states that the endpoint of "Occurrence of post-surgical major bleeding, as defined by International Society on Thrombosis and Hemostasis (ISTH) criteria" should be assessed "within 12 hours after the end of the initial surgery." This endpoint will be changed to read as follows: "Occurrence of post-surgical major bleeding, as defined by International Society on Thrombosis and hemostasis (ISTH) criteria within 12 hours after the start of the initial surgery."

Rationale: There is a typo in the main body of current protocol (section 11.5.2.3) for this endpoint. The wording of the endpoint will be changed to be consistent with protocol synopsis for this endpoint.

If there any questions concerning these changes, please contact us. These changes will also be captured in any future protocol amendment.

PPD

PPD

Director, Clinical Development
Alexion Pharmaceuticals, Inc

Phone: PPD

Email: PPD

Protocol 19-515
Intraoperative
Hemostasis Assessment Form

Investigator is responsible for evaluating the endpoint of hemostatic efficacy. The Investigator will consult with the research team and surgical team, if applicable, and will be responsible for the interpretation of the endpoint prior to completing the hemostatic efficacy form.

Please complete this form and this will serve as a source document and be provided to the Endpoint Adjudication Committee.

- Estimate blood loss based on a particular surgery or surgery type
- Hemostasis evaluation period is from start of surgery to end of surgery, however hemostasis assessment is recorded at the end of the surgery
- **Predicted Blood Loss (mL):** Before an operation/incision, the Predicted Blood Loss should be estimated for an ANTI coagulated patient based on previous experience, this is a subjective evaluation
- **Observed Blood Loss (mL):** Register the actual amount of blood **in ml** which was lost during the operation.
- **Hemostasis Assessment** – This is subjective Hemostasis Assessment to be compared against normal non-anti-coagulated situations based on the 4-items scale (from excellent to poor)

Hemostasis Assessment

Subject Number		Staff Completing Form	
Date entry into operation room		Time entry into operating room (24 Hr Clock)	
Type of surgical intervention		Predicted Blood Loss (mL) Determined prior to first incision	
Start date of surgery		Start time of surgery (24 Hr)	
End date of surgery		End time of surgery (24 Hr)	
Date of exit from operating room		Time of exit from operating room (24 Hr)	

Hemostatic Efficacy: Investigator Assessment – Treatment Day 1

Was there any unexpected blood loss due to surgical complications	 Yes, comment:  No	Observed Blood Loss (mL) Determined at end of surgery	
Date of Hemostasis Assessment		Time of Hemostasis Assessment	
Category	Definition		Investigator Assessment (check only 1 category)
Excellent	Normal hemostasis during the procedure		
Good	Mildly abnormal hemostasis as judged by quantity of blood loss (e.g. slight oozing from surgical wounds)		
Moderate	Moderate abnormality in intraprocedural hemostasis (e.g. controllable bleeding) but no need for additional systemic procoagulant product		
Poor	Severe hemostatic abnormality during the procedure (e.g. severe refractory hemorrhage) and need for additional systemic procoagulant products		
Investigator Name:	Signature:		Date:

1 April 2021

Protocol: 19-515 Protocol Amendment #2: 20 July 2020

Administrative Change Letter #1

Reason for Letter: Provide clarification that the adverse event (AE) selection in the CRF is different from the protocol and antibodies against host cell proteins (HCPs) are not being measured and analyzed.

To those sites participating in the above named and numbered clinical study, this letter serves to inform you about the following administrative changes to the above referenced protocol version.

Clarification: Section 9.2.2. Assessment of Causal Relationship

- Removal of causality assessment categories; probably, possible, unlikely, unrelated
- Causality to be assessed on a binary scale of related and unrelated

Rationale: Standardizing collection of severity and causality according to Alexion Global Drug Safety Standards.

Clarification: Section 9.2.3. Assessment of Severity

- Removal of Grades
- Removal of 'life-threatening consequence or urgent intervention indicated'.
- Removal of 'event results in Death'.

Rationale: Standardizing collection of severity and causality of AEs according to CDISC/CDASH guidelines. "Life-threatening" events are collected using a separate variable on the adverse event form. Death is collected as an outcome.

Clarification: Section 10.2.5., 11.7.7., Schedule of Assessments

Antibodies against HCPs are not being determined for the study.

Rationale: A Generation 2 HCP assay has not been developed. Results from previous studies indicate that the immunogenicity is low, therefore there is no value in continuing the assay.

Please file this letter and any IRB/EC correspondence with all copies of the protocol in the Investigator Site File and in all pertinent repositories in which the protocol is maintained.

If there are any questions concerning these changes, please contact us. These changes will also be captured in any future protocol amendment.

PPD

PPD

Global Medical Director Hematology

Alexion Pharmaceuticals, Inc

Phone: PPD Email: PPD

Protocol 19-515:

PROSPECTIVE, OPEN-LABEL STUDY OF ANDEXANET ALFA IN PATIENTS RECEIVING A FACTOR XA INHIBITOR WHO REQUIRE URGENT SURGERY (ANNEXA-S)

Protocol Amendment 2.1 (Japan)

MEDICAL MONITOR :

PPD [REDACTED], MD
Director, Clinical Development
Alexion Pharmaceuticals, Inc.
Phone: PPD [REDACTED]
Fax: PPD [REDACTED]
email: PPD [REDACTED]

PROTOCOL DATE :

Original: 16 September 2019
Amendment 1: 19 November 2019
Amendment 2: 20 July 2020
Amendment 2.1 (Japan): 15 March 2021

SPONSOR SIGNATORY :

PPD [REDACTED]
[REDACTED] ————— DATE
Director, Clinical Development

15-Mar-2021 | 19:50:55 EDT

Confidentiality Statement

This protocol is the property of the Sponsor. It is a confidential communication. Acceptance implies an agreement not to disclose information contained herein that is not otherwise publicly available, with the exception that it may be disclosed to an Institutional Review Board (IRB)/Independent Ethics Committee (IEC) for the purpose of obtaining approval to conduct the study. The IRB/IEC is requested and expected to maintain confidentiality. This document may not be used or published without the consent of the Sponsor.

INVESTIGATOR'S AGREEMENT

I have read the attached protocol amendment and agree to abide by all provisions set forth therein.

I agree to comply with the International Council on Harmonisation of Technical Requirements for Pharmaceuticals for Human Use Tripartite Guideline on Good Clinical Practice (GCP) and applicable Food and Drug Administration (FDA) regulations/guidelines set forth in 21 Code of Federal Regulations (CFR) Parts 11, 50, 54, 56, and 312, applicable Health Canada regulations/guidelines and all locally applicable laws.

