4.0 SELECTION OF STUDY POPULATION AND CRITERIA FOR WITHDRAWAL

4.1. Inclusion Criteria

All of the following criteria must be met for the patient to be eligible to participate in the study:

1. Either the patient or his or her medical proxy (or legal designee) has given written informed consent prior to Screening.
2. Age ≥ 18 and < 85 years old.
3. Requires urgent surgical intervention that must occur within 12 hours of consent, for which reversal of anti-fXa activity is judged necessary.
4. Treatment with an oral FXa inhibitor (apixaban [last dose 2.5 mg or greater], rivaroxaban [last dose 10 mg or greater], edoxaban [last dose 30 mg or greater] or enoxaparin [≥ 1 mg/kg/d]):
 - a. ≤ 15 hours prior to start of surgery.
 - b. > 15 hours prior to start of surgery or unknown time from the last dose, if documented anti fXa activity is > 100 ng/mL (> 0.5 IU/mL for enoxaparin, or over the equivalent IU/mL threshold on a low molecular weight heparin assay; see Laboratory Manual) within 2 hours prior to consent. Note: Patients enrolled in this manner should receive a high-andexanet dosing regimen.
5. Have a negative pregnancy test documented prior to enrollment (for women of childbearing potential).
6. Willingness to use highly effective methods of contraception [31] through 30 days following study drug dose (for female and male patients who are fertile).

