4.2. Exclusion Criteria

If a patient meets any of the following criteria, he or she is *not* eligible to participate:

1. Surgery for which the risk of clinically meaningful uncontrolled or unmanageable bleeding is low.
2. Acute life-threatening bleeding (ISTH criteria [32]) at the time of Screening:
 - a. The patient has acute-overt bleeding that is potentially life-threatening, e.g., with signs or symptoms of hemodynamic compromise, such as severe hypotension, poor skin perfusion, mental confusion, low urine output that cannot be otherwise explained.
 - b. The patient has overt bleeding associated with a fall in hemoglobin level by ≥ 2 g/dL, OR, a hemoglobin ≤ 8 g/dL if no baseline hemoglobin is available.
 - c. The patient has acute bleeding in a critical area or organ, such as pericardial, intracranial, or intraspinal.

3. Any surgical procedure that involves the intraoperative use of systemic, intravascular, unfractionated heparin.
4. Primary procedure being considered for efficacy evaluation is a non-surgical interventional procedure (e.g., skin biopsy, lumbar puncture, cardiac catheterization, endoscopic retrograde cholangio-pancreatography).
5. Expected survival of < 1 month due to comorbidity.
6. Known “Do Not Resuscitate” order or similar advanced directive.
7. The patient has a recent history (within 30 days prior to Screening) of a diagnosed TE as follows: VTE (including DVT, PE, intracardiac thrombus); MI (including asymptomatic troponin elevations); disseminated intravascular coagulation (DIC); acute traumatic coagulopathy; cerebrovascular accident; transient ischemic attack; unstable angina pectoris hospitalization; or severe peripheral vascular disease (see [Appendix B](#) for DIC scoring algorithm).
8. Acute decompensated heart failure or cardiogenic shock at the time of screening (see [Appendix C](#) for cardiogenic shock definition).
9. The patient has sepsis or septic or hemorrhagic shock at the time of Screening (see definition in Appendix C).
10. The patient has heparin-induced thrombocytopenia (with or without thrombosis).
11. Inherited coagulopathy (e.g., anti-phospholipid antibody syndrome, protein C/S deficiency, Factor V Leiden) at time of Screening.
12. Platelet count < 80,000/ μ L at the time of Screening.
13. Last dose of apixaban < 2.5 mg, rivaroxaban < 10 mg, edoxaban < 30 mg, enoxaparin < 40 mg.
14. The patient is pregnant or a lactating female.

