10.1.7. Eligibility Assessment

Following completion of assessments and screening testing, the investigator will determine eligibility of the patient by comparing results to inclusion and exclusion criteria. Note: It is the Sponsor's policy not to grant exceptions or waivers for inclusion and exclusion criteria.

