11.3. Analysis Populations

11.3.1. Enrolled Population

The enrolled population will consist of all patients enrolled (signed informed consent and met inclusion/exclusion criteria) into the study irrespective of whether they received andexanet or not.

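### At Japanese sites the dosing table provides for last edoxaban doses from 15 mg to below 30 mg, which the unchanged eligibility criteria exclude

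*Protocol*

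**What the plan says.** **Dosing.** Amendment 2.2 (Japan), dated 30 August 2021, gives its reason as "Update necessitated from reconsideration of andexanet dosage in edoxaban 15-30 mg treated Japanese patients" and says this group will be given the high-dose regimen. Its summary of changes reads "Edoxaban 15 mg-60 mg: High dose andexanet alfa" for a last dose taken less than 8 hours before. The revised synopsis table and Section 6.2 Table 2 carry the same range. On scope it states: "This country-specific amendment changed a part of the protocol contents and applies to all subjects enrolled in Japan".

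**Eligibility.** Section 4.1, inclusion criterion 4, requires "edoxaban [last dose 30 mg or greater". Section 4.2, exclusion criterion 13, lists "edoxaban < 30 mg, enoxaparin < 40 mg" among the last doses that exclude a patient. The synopsis sets the same 30 mg edoxaban minimum in both lists. Section 10.1.7 records a sponsor "policy not to grant exceptions or waivers for inclusion and exclusion criteria".

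**Analysis populations.** Section 11.3.1 defines the Enrolled Population as "all patients enrolled (signed informed consent and met inclusion/exclusion criteria) into the study". The Safety Analysis Population (11.3.2) is those enrolled and given any andexanet. The Efficacy Analysis Population (11.3.3) is likewise drawn from enrolled patients, with further conditions on surgery and baseline anti-fXa activity.

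**The concern.** A Japanese investigator with a patient whose last edoxaban dose was 15 mg finds a regimen for that patient in the dosing table and an amendment saying such patients will be treated. The same investigator finds two criteria saying the patient may not enter. The decision is made within hours, before urgent surgery, and no waiver is available to settle it.

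If the site follows Section 4, patients in this range contribute nothing and that part of the dosing row is idle. If the site follows the amendment's rationale, a patient who fails an inclusion criterion and meets an exclusion criterion receives study drug. It is then unclear where that patient is counted, and this includes the thrombotic events that Section 9.1.3 names as the adverse events of special interest.

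**Working it through.** **1. Are both texts in force together?** Amendment 2.2 is later than Amendment 2 (20 July 2020) and changes only part of it for Japan. Whatever it leaves alone still applies there, so this is not a comparison with superseded text.

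**2. Do the Japan amendments change eligibility?** The 2.2 summary lists three items: the synopsis dosing item, Section 6.2 Table 2 and Section 9.2.2. Its detailed list goes from page 22 to page 54, whereas Sections 4.1 and 4.2 start at page 44 in the table of contents. The visible part of the Amendment 2.1 list runs from the synopsis dosing table to page 54 and then page 63, again passing over Section 4. The edoxaban entries in the 2.2 'before' tables (30 mg low, 60 mg high) are those of global Amendment 2. So 2.2 restates the Japanese dosing changes against the global text and alters no criterion.

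**3. Compare the dose ranges.**

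| Last edoxaban dose, taken < 8 h before | Japan dosing table | Inclusion 4 | Exclusion 13 |
|---|---|---|---|
| 15 mg to < 30 mg | high dose | not met | met (excluded) |
| 30 mg to 60 mg | high dose | met | not met |

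The table covers 15-60 mg and eligibility covers 30 mg and above. They agree on 30-60 mg and conflict on 15 mg to below 30 mg.

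**4. Where would a treated patient in the conflicting range be counted?** Enrolment requires the criteria to be met (Sections 10.1.8 and 11.3.1), so the patient is not in the Enrolled Population. The Safety and Efficacy Analysis Populations both require enrolment. Literally read, the patient is in 0 of 3 populations.

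**5. Effect on precision.** The plan's own figure comes first. Section 11.6 has 100 enrolled with 20% attrition, so 100 × (1 − 0.20) = 80, and claims a 95% half-width below 11%. The worst-case Wald half-width is 1.96 × √(0.5 × 0.5 / 80) = 0.1096, or 10.96%, so the claim is reproduced. Now suppose k of the 80 are lost. The documents give no k, so these values are assumptions:

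| k | n | half-width at p = 0.5 |
|---|---|---|
| 0 | 80 | 10.96% |
| 1 | 79 | 11.03% |
| 2 | 78 | 11.10% |
| 5 | 75 | 11.32% |
| 10 | 70 | 11.71% |

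At p = 0.819, the rate the protocol reports for its earlier bleeding study (Section 1.4.7), the half-width goes from 8.4% at n = 80 to 9.0% at n = 70. The change is small either way.

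**The case against.** The best reply is that eligibility is settled before dosing and a dosing row admits nobody. A site that applies Section 4 first, with no waivers, breaches nothing and never reaches the 15 mg entry. The same Japan tables keep enoxaparin rows while noting that enoxaparin is out of scope there, so an unused row has a precedent. This has force: the table alone does not tell a site to enrol an ineligible patient. It does not remove the contradiction. The enoxaparin rows carry an explicit note and the 15 mg entry carries none. The amendment also goes beyond listing a row, since its stated purpose is to treat the 15-30 mg group. Moreover, Amendment 2 added apixaban 2.5 mg to Table 2 expressly to match exclusion criterion 13, so the sponsor has already treated agreement between these two places as necessary.

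Three stronger readings are tempting and are not supported:

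- *The group the amendment was written for contributes no data.* That group includes patients at 30 mg, who are eligible and dosed. The study cited for the change was in subjects taking 30 mg.
- *Each affected patient costs 1/80 = 1.25% of the primary denominator.* The documents give no count of Japanese patients or of those on 15 mg. A patient would also need surgery and a central baseline anti-fXa activity of at least 75 ng/mL to be in that denominator.
- *The Japan table itself removes safety data.* The gap comes from the population definitions and would affect any treated patient later found ineligible. Collection continues regardless: Section 9.2.1 requires treatment-emergent events to be reported for 30 days after the last dose, and the DSMB reviews all safety data. The risk is to the defined summaries, and it rests on a literal reading that a site or the SAP might not follow.

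One limit remains. The opening of the Amendment 2.1 change list and the second part of the document are not in the text at hand, so a change there to the synopsis criteria cannot be fully excluded. That would not repair Sections 4.1 and 4.2, which the visible page order skips.

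**Conclusion.** The contradiction stands for last edoxaban doses from 15 mg to below 30 mg, taken less than 8 hours before, at Japanese sites. It does not extend to 30 mg and above. It rests on the Amendment 2.2 change list being complete as printed, and on no unseen Japan text altering criteria 4 and 13.

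Its size in patients is unknown, and its effect on the primary estimate is probably small. It needs correcting because the protocol gives opposing instructions on who may receive study drug. The second consequence, that a patient treated in this range is in none of the defined populations, holds on the literal definitions only.

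**What to change.** 1. Reconcile inclusion criterion 4 and exclusion criterion 13 (synopsis and Sections 4.1 and 4.2) with the Japan dosing table (synopsis and Section 6.2 Table 2), so that the lowest edoxaban dose is the same throughout. This can be done by Japan-specific criteria or by changing the table. Which threshold is right is for the sponsor.
2. Check Japanese enrolment to date for anyone treated after a last edoxaban dose below 30 mg, and state in which analysis populations they are counted.
3. Define the Safety Analysis Population in Section 11.3.2 as all patients who received any andexanet, whatever their eligibility. This protects safety reporting for every treated patient later found ineligible, in Japan or elsewhere.

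The cost is one page of country-specific amendment, one sentence in Section 11.3.2 and a check of Japanese enrolment records. The sample size and the analysis methods do not change.
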